#### **6.3.7** ECG

Twelve-lead ECGs will be recorded at the time points indicated in the study plan (Table 1 and Table 2).

Electrocardiograms will be recorded in the supine position after the volunteer has rested in this position for at least 10 minutes.

Only the overall evaluation (normal/abnormal) will be captured in the eCRF. Any abnormalities (including QTcB values) should be reviewed by an appropriately qualified person.

The original ECG printouts with variables must be signed and dated and stored in the volunteer's source workbook as source data.

#### 6.3.8 Vital signs

Vital signs assessment will be performed at the time indicated in (Table 1 and Table 2).

#### 6.3.8.1 Pulse rate and supine blood pressure

Supine blood pressure and pulse rate will be measured using standard equipment after 10 minutes rest on a bed. Additional blood pressure/pulse rate assessments may be taken for safety at the discretion of the Principal Investigator or delegate.

## 6.3.8.2 Height and weight

Height (cm) and weight (kg) will be evaluated at screening and BMI (kg/m²) will be calculated. Height will be measured at screening only; weight will be measured at the times shown in Table 1. The volunteers will be required to remove their shoes and wear light indoor clothing for these measurements. When requested or judged necessary for the program, body weight and/or BMI can be measured at additional time points.

#### 6.3.9 Ophthalmology

A baseline ophthalmological examination will be performed at the time indicated in the study plan (Table 1), including assessments of best corrected visual acuity and slit lamp fundoscopy and intraocular pressure measurement.

A full ophthalmologic examination including a slit-lamp fundoscopy, should be performed if a volunteer experiences any visual symptoms (such as dry eyes, grittiness, or irritation including blurring of vision), with additional tests if clinically indicated.

Any clinically significant findings, including those confirmed by the ophthalmologist must be reported as an AE. Photographs should be performed to record any clinically significant findings. These photographs should be available for central review by AstraZeneca and AstraZeneca representatives if necessary.

Any volunteer who develops corneal ulceration will be immediately withdrawn from study participation and the abnormality followed up by an ophthalmologist until resolution.

#### 6.4 Pharmacokinetics

## 6.4.1 Collection of samples

Venous blood samples for determination of concentrations of AZD9291 and its metabolites (AZ5104 and AZ7550) will be taken at the time points detailed in the study plan (Table 1) and the PK sampling schedule (Table 2). Every attempt should be made to collect all samples at the times specified in the PK sampling schedule. The actual time and date of collection of each blood sample must be recorded in the eCRF. Samples will be collected, processed, labelled, and shipped for analysis as detailed in the Laboratory Manual.

A 30-minute window will be allowed for samples taken at pre-dose; a 5-minute window will be allowed for samples taken up to and including 1 hour; a 15-minute window for samples taken at 2 to 12 hours and a 2-hour window for samples taken from 24 to 72 hours onwards. The samples collected after 72 hours may have a 1-day window.

Samples will be collected, labelled stored and shipped as detailed in Laboratory Manual.

For blood volume see Section 7.1.

## 6.4.2 Determination of drug concentration

Samples for determination of AZD9291 and its metabolites (AZ5104 and AZ7550) will be analysed by on behalf of the Clinical Bioanalysis Alliance, AstraZeneca R&D, using appropriate bioanalytical methods. Full details of the bioanalytical methods used will be described in a separate bioanalytical report. All samples still within the known stability of the analytes of interest (ie, AZD9291 and its metabolites AZ5104 and AZ7550) at the time of receipt by the bioanalytical laboratory will be analysed.

# 6.5 Pharmacogenetics

Volunteers will be offered the possibility to participate in optional genetic exploratory research. After signing a separate consent for optional genetic research, a blood sample will be collected in accordance with the inclusion criteria and study plan.

If for any reason the blood sample is not drawn on Day -1 of Period 1, according to the study plan, it may be taken at any time up until the last study visit. Although genotype is a stable parameter, early sample collection is preferred to avoid introducing bias through excluding volunteers who may withdraw due to an AE, such volunteers would be important to include in any genetic analysis. Only 1 sample should be collected per volunteer for genetic research during the study.

A record of the date the volunteer consented to the genetic research and the date of the blood sample collection will be recorded in the appropriate section of the EDC system. Samples will be collected, handled, labelled, stored, and shipped as detailed in Laboratory Manual.

For pharmacogenetic blood sampling volume see Section 7.1.

### 7. BIOLOGICAL SAMPLING PROCEDURES

#### 7.1 Volume of blood

The total volume of blood that will be drawn from each volunteer in this study is as follows:

Table 4 Volume of blood to be drawn from each subject

Assessment		Sample volume (mL)	No. of samples	Total volume (mL)
Safety	Clinical chemistry	5	12	60
	Hematology	2	12	24
	Serology	3.5	1	3.5
Pharmacokinetic		2	38	76
Pharmacogenetic b		10	1	10
Total				173.5

a If using an indwelling catheter, 1.0 mL of blood will be removed to flush the catheter prior to each serial PK sample collection time point (up to 48 hours of inpatient sampling only)

# 7.2 Handling, storage and destruction of biological samples

The samples will be used up or disposed of after analyses or retained for further use as described here.

#### 7.2.1 Pharmacokinetic and/or pharmacodynamic samples

Pharmacokinetic samples will be disposed of after the Bioanalytical Report finalisation or 6 months after issuance of the draft Bioanalytical Report (whichever is earlier), unless requested for future analyses.

b The pharmacogenetic sample is optional

Pharmacokinetic samples may be disposed of or destroyed and anonymized by pooling. Additional analyses may be conducted on the anonymized, pooled PK samples to further evaluate and validate the analytical method. Any results from such analyses may be reported separately from the CSR.

Incurred sample reproducibility analysis, if any, will be performed alongside the bioanalysis of the test samples. The results from the evaluation will not be reported in the CSR but separately in a Bioanalytical Report.

Any residual back-up PK samples may be used for future exploratory biomarker research (in this case, residual back-up PK samples will be shipped to AZ Biobank; see details in the Laboratory Manual).

## 7.2.2 Pharmacogenetic samples

The processes adopted for the coding and storage of samples for genetic analysis are important to maintain volunteer confidentiality. Samples will be stored for a maximum of 15 years, from the date of the last volunteer's last visit, after which they will be destroyed. Deoxyribonucleic acid (DNA) is a finite resource that may be used up during analyses. Samples will be stored and used until no further analyses are possible or up to the maximum storage time has been reached.

For all samples, irrespective of the type of coding used, the DNA will be extracted from the blood sample. The DNA sample will be assigned a unique number replacing the information on the sample tube. Thereafter, the DNA sample will be identifiable by the unique DNA number only. The DNA number is used to identify the sample and corresponding data at the AstraZeneca genetics laboratories, or at the designated contract laboratory. No personal details identifying the individual will be available to any person (AstraZeneca employee or contract laboratory personnel working with the DNA).

The samples and data for genetic analysis in this study will be single coded. The link between the volunteer enrolment/randomisation code and the DNA number will be maintained and stored in a secure environment, with restricted access within the Clinical Genotyping Group Laboratory Information Management System (LIMS) at AstraZeneca. The link will be used to identify the relevant DNA samples for analysis, facilitate correlation of genotypic results with clinical data, allow regulatory audit and to trace samples for destruction in the case of withdrawal of consent when the volunteer has requested disposal/destruction of collected samples not yet analysed.

# 7.3 Labelling and shipment of biohazard samples

The Principal Investigator ensures that samples are labelled and shipped in accordance with the Laboratory Manual and the Biological Substance, Category B Regulations (materials containing or suspected to contain infectious substances that do not meet Category A criteria), see Appendix C 'IATA 6.2 Guidance Document'.

Any samples identified as Infectious Category A materials are not shipped and no further samples will be taken from the volunteer unless agreed with AstraZeneca and appropriate labelling, shipment and containment provisions are approved.

# 7.4 Chain of custody of biological samples

A full chain of custody is maintained for all samples throughout their lifecycle.

The Principal Investigator keeps full traceability of collected biological samples from the volunteers while in storage at the center until shipment or disposal (where appropriate) and keeps documentation of receipt of arrival.

The sample receiver keeps full traceability of the samples while in storage and during use until used or disposed of or until further shipment and keeps documentation of receipt of arrival.

AstraZeneca keeps oversight of the entire life cycle through internal procedures, monitoring of study sites and auditing of external laboratory providers.

Samples retained for further use are registered in the AstraZeneca biobank system during the entire life cycle.

# 7.5 Withdrawal of informed consent for donated biological samples

If a volunteer withdraws consent to the use of donated biological samples, the samples will be disposed of/destroyed, and the action documented. If samples are already analysed, AstraZeneca is not obliged to destroy the results of this research.

As collection of the biological samples is an integral part of the study, then the volunteer is withdrawn from further study participation.

The Principal Investigator:

- Ensures volunteers' withdrawal of informed consent to the use of donated samples is notified immediately to AstraZeneca
- Ensures that biological samples from that volunteer, if stored at the study site, are immediately identified, disposed of /destroyed, and the action documented
- Ensures the laboratory(ies) holding the samples is/are informed about the withdrawn consent immediately and that samples are disposed/destroyed, the action documented and the signed document returned to the study site
- Ensures that the volunteer and AstraZeneca are informed about the sample disposal

AstraZeneca ensures the central laboratory(ies) holding the samples is/are informed about the withdrawn consent immediately and that samples are disposed of/destroyed and the action documented and returned to the study site.

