#### Optional pharmacogenetic testing inclusion criteria

Provision of signed, written and dated informed consent for optional genetic/biomarker research is required. If a volunteer declines to participate in the genetic component of the study, there will be no penalty or loss of benefit to the volunteer. The volunteer will not be excluded from other aspects of the study described in this protocol.

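### Section 7.5 withdraws from the study anyone who retracts sample consent and makes no exception for the optional pharmacogenetic sample

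*Protocol*

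**What the plan says.** Protocol Section 7.5 opens with an unqualified trigger: "If a volunteer withdraws consent to the use of donated biological samples, the samples will be disposed of/destroyed, and the action documented". It then gives the consequence for the volunteer: "As collection of the biological samples is an integral part of the study, then the volunteer is withdrawn from further study participation". The section neither names the genetic sample nor exempts it.

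Elsewhere the genetic sample is treated as separate from the main study:

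- Section 4.1, on optional pharmacogenetic testing: "If a volunteer declines to participate in the genetic component of the study, there will be no penalty or loss of benefit" to the volunteer, and "The volunteer will not be excluded from other aspects of the study described in this protocol".
- Section 6.5: "After signing a separate consent for optional genetic research, a blood sample will be collected".
- Footnote b to Table 4 (Section 7.1): "The pharmacogenetic sample is optional".
- Section 7.2.2 explains that the link between volunteer code and DNA number is kept, among other purposes, "to trace samples for destruction in the case of withdrawal of consent when the volunteer has requested disposal/destruction of collected samples not yet analysed". It says nothing about leaving the study.
- Section 2.4 makes the genetic sample an exploratory objective, reported outside the clinical study report.

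**The concern.** The reason in Section 7.5 holds for PK and safety laboratory samples, because without them the study cannot meet its objectives for that volunteer. It does not hold for a sample that the protocol itself calls optional. A volunteer who refuses genetics at screening stays in the study. One who agrees on Day -1 of Period 1 and changes his mind a week later would, if the site follows Section 7.5 literally, be removed. No study purpose explains the difference.

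Two things are at stake. The first is consent: a site applying the text as written would attach a consequence to retracting an optional consent. The second is data: the comparison is within volunteer, and Section 3.1 counts a volunteer as evaluable only if the required PK collections are complete in both periods. Removing a willing volunteer partway through can cost a pair.

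**Working it through.** **Step 1: does Section 7.5 reach the genetic sample?**

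| Question | Section 7.5 | Rest of the protocol |
|---|---|---|
| Which samples? | Donated biological samples, unqualified | Section 7 covers two stored types, PK (7.2.1) and pharmacogenetic (7.2.2); Table 4 lists both |
| Is the sample integral? | Yes, given as the reason | Genetic sample optional (4.1, 6.5, Table 4) |
| Which consent? | Not specified | Separate genetic consent (6.5; Table 1 note m) |
| What follows retraction? | Destruction and study withdrawal | Genetic sample: tracing and destruction (7.2.2) |
| What follows refusal at entry? | Not covered | Stays in the study (4.1) |

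Section 7.5 closes the chapter that covers both types and does not narrow its scope. Section 7.2.2 shows that retraction of genetic consent is foreseen. A site facing that event finds a procedure for it only in Section 7.5, and that procedure ends in withdrawal. The literal reading therefore includes the genetic sample, but by inference from unqualified wording.

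**Step 2: when would a pair be lost?**

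Section 6.5 plans the genetic sample for Day -1 of Period 1, before any dosing, but allows it up to the last visit. A retraction after the early sample and before the 504-hour sample of Period 2 would leave the volunteer without a complete pair. A retraction after that point costs no pair.

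**Step 3: what is a lost pair worth?**

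Inputs from Section 12.3: within-subject CV 23% for both parameters, a 5% change, limits 80 to 125%, 40 evaluable, about 20% withdrawal. Stated power is 95% per parameter and 90% for both.

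- Log-scale SD = sqrt(ln(1 + 0.23²)) = sqrt(0.0515) = 0.227.
- SE of the paired difference = 0.227 × sqrt(2/40) = 0.0508.
- Two one-sided tests at 5% each, limits ln 0.80 and ln 1.25, n − 1 degrees of freedom, integrating over the variance estimate.
- Power per parameter at n = 40: 95.3% (ratio 0.95) or 95.8% (ratio 1.05). The stated 95% reproduces.
- Joint power as the product of the two (treating them as independent): 90.9% or 91.8%. Without independence the lower bound at ratio 0.95 is 2p − 1 = 90.7%. The stated 90% reproduces.
- Enrolment: 40 / (1 − 0.20) = 50, which leaves a margin of 50 − 40 = 10.

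Fewer pairs, at ratio 0.95 and CV 23% for both parameters:

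| Evaluable pairs | Per parameter | Joint |
|---|---|---|
| 40 | 95.3% | 90.9% |
| 39 | 94.9% | 90.1% |
| 38 | 94.4% | 89.2% |
| 37 | 93.9% | 88.2% |
| 36 | 93.3% | 87.1% |

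Each pair lost below 40 costs about one percentage point of joint power, and only once more than 10 of 50 volunteers have been lost for all reasons together.

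**The case against.** The strongest reply is that Section 7.5 never mentions genetics and carries its own limit. It bases withdrawal on the samples being integral, and an optional sample fails that test. With the separate consent in Section 6.5 and the destruction-only handling in Section 7.2.2, a sensible reader would confine Section 7.5 to required samples. The separate genetic consent form, which is not part of the documents at hand, may also say so.

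Much of this stands. The narrower reading is reasonable and may well be what was meant. But the clause about integral samples is written as a statement of fact about all the samples covered, not as a condition for a site to test, and the trigger sentence before it is unqualified. An instruction to sites should not depend on that inference.

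Several stronger readings are tempting, and the documents do not support them:

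- A reader might infer that Section 4.1 flatly contradicts Section 7.5. Section 4.1 covers a volunteer who declines and is silent on later retraction. The conflict is with its intent and with the optional status of the sample.
- A reader might extend the point to residual back-up PK samples kept for exploratory research. Section 7.2.1 describes no separate consent for that use which could be retracted on its own.
- A reader might infer that every retraction costs a pair. That depends on timing (step 2).
- A reader might infer that safety information is lost. Section 5.9 has adverse events followed up after withdrawal, and Section 12.2.1 keeps data up to discontinuation in the analyses.

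**Conclusion.** The point holds as an inconsistency between a mandatory rule and the protocol's own description of an optional component. Section 7.5, taken literally, would withdraw a volunteer who retracts only the genetic consent, for a reason that is untrue of that sample. Sections 4.1 and 7.2.2 point the other way.

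Its size is small. If retraction came before Period 2 sampling was complete, the cost would be one paired profile, 1/40 = 2.5% of the evaluable target. The documents give no rate of retraction, so no expected loss can be stated, and the withdrawal allowance would absorb a few cases. A reader might conclude that the sample size is threatened; it is not. The stated power and the enrolment of 50 both reproduce.

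The conclusion rests on reading the wording of Section 7.5 as written and on the absence of any exception elsewhere in the protocol. For retracted consent to required PK samples, the rule has a clear study reason and is not criticised here.

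**What to change.** Reconcile Section 7.5 with Sections 4.1 and 7.2.2. Limit the study-withdrawal consequence in Section 7.5 to samples required for the study objectives, namely PK and safety laboratory samples. Add that retracting consent for the optional pharmacogenetic sample leads to destruction of that sample and is not in itself a reason for withdrawal from the study. Section 4.1 could cover later retraction as well as refusal, so that the two places agree.

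The cost is one or two sentences in the protocol and matching wording in the consent form, handled through the change procedure in Section 8.5. It needs no extra volunteers or procedures and no change to the sample size.

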# 8. ETHICAL AND REGULATORY REQUIREMENTS

# 8.1 Ethical conduct of the study

The study will be performed in accordance with ethical principles that have their origin in the Declaration of Helsinki and are consistent with International Conference on Harmonisation (ICH)/Good Clinical Practice (GCP), applicable regulatory requirements and the AstraZeneca policy on Bioethics and Human Biological Samples.

# 8.2 Subject data protection

The Informed Consent Form will incorporate (or, in some cases, be accompanied by a separate document incorporating) wording that complies with relevant data protection and privacy legislation.

# 8.3 Ethics and regulatory review

An Institutional Review Board should approve the final study protocol, including the final version of the Informed Consent Form and any other written information and/or materials to be provided to the volunteers. The investigator will ensure the distribution of these documents to the applicable Institutional Review Board, and to the study site staff.

The opinion of the Institutional Review Board should be given in writing. The investigator should submit the written approval to AstraZeneca before enrolment of any volunteer into the study.

The Institutional Review Board should approve all advertising used to recruit volunteers for the study.

AstraZeneca should approve any modifications to the Informed Consent Form that are needed to meet local requirements.

If required by local regulations, the protocol should be re-approved by the Institutional Review Board annually.

Before enrolment of any volunteer into the study, the final study protocol, including the final version of the Informed Consent Form, is approved by the national regulatory authority or a notification to the national regulatory authority is done, according to local regulations.

AstraZeneca will handle the distribution of any of these documents to the national regulatory authorities.

AstraZeneca will provide Regulatory Authorities, Institutional Review Board and Principal Investigators with safety updates/reports according to local requirements, including Suspected Unexpected Serious Adverse Reactions (SUSARs), where relevant.

#### 8.4 Informed consent

The Principal Investigator(s) or designee will:

- Ensure each volunteer is given full and adequate oral and written information about the nature, purpose, possible risk and benefit of the study
- Ensure each volunteer is notified that they are free to discontinue from the study at any time
- Ensure that each volunteer is given the opportunity to ask questions and allowed time to consider the information provided
- Ensure each volunteer provides signed and dated informed consent before conducting any procedure specifically for the study
- Ensure the original, signed Informed Consent Form(s) is/are stored in the Investigator's Study File
- Ensure a copy of the signed Informed Consent Form is given to the volunteer
- Ensure that any incentives for volunteers who participate in the study as well as any
  provisions for volunteers harmed as a consequence of study participation are
  described in the informed consent form that is approved by an Institutional Review
  Board

# 8.5 Changes to the protocol and informed consent form

Study procedures will not be changed without the mutual agreement of the Principal Investigator and AstraZeneca.

If there are any substantial changes to the CSP, then these changes will be documented in a CSP amendment and where required in a new version of the study protocol (Revised CSP).

The amendment is to be approved by the relevant Institutional Review Board and if applicable, also the national regulatory authority approval, before implementation. Local requirements are to be followed for revised protocols.

AstraZeneca will distribute any subsequent amendments and new versions of the protocol to each Principal Investigator(s). For distribution to Institutional Review Board see Section 8.3.

If a protocol amendment requires a change to a center's Informed Consent Form, AstraZeneca and the center's Institutional Review Board are to approve the revised Informed Consent Form before the revised form is used.

If local regulations require, any administrative change will be communicated to or approved by each Institutional Review Board.

